### 2.6.4. Visit 5/Study Exit (Day 56) – Telephone Follow-Up

Subject will be contacted via telephone and data collected since their last visit per the schedule of events. Any changes in concomitant medications/concurrent procedures will be assessed. Any anticipated observations, adverse events, and/or SAE/UADE of the previous treatment site(s) will be documented.

If the treatment effect remains at Day 56 the subject will be followed every four (4) weeks via telephone until Day 84. Any clinically significant adverse event will be followed until resolution. The subject will exit the study after Day 56 once there is no longer a treatment effect or the Day 84 follow-up is completed and no ongoing clinically significant events.

Study exit data will be collected and the subject reminded to contact the investigator if any new previously unreported event occurs as it related to the treatment.

A subject is considered to have exited (a completer) the study after completing all scheduled visits. In the event that a subject does not attend a scheduled visit every effort will be made to reschedule and those efforts will be documented. In the event of a subject lost to follow-up a study exit will be completed.

If a subject decides to withdraw participation early, the subject will be requested to complete a final study visit and exit the study. The investigator or sponsor may at any time during the study remove a subject if there is any potential safety issue or extreme non-compliance. In all cases every attempt will be made to complete a final study visit.

### 3. Outcome Measures and Assessments

Outcome measures will be assessed around multiple endpoints. These measures will be: pain, function, range of motion, anticipated observations, duration of improvement, and safety. Additional assessments may also be taken but not part of analysis (i.e. subject post-treatment questionnaire). The specific assessment tools, collection method and time points are listed herein.

### 3.1.1. Primary Outcome Measure

Improvement of knee pain as measured on the Visual Analog Scale (VAS) for pain at Day 7 as compared to baseline (Day 0). See Appendix.

### 3.1.2. Secondary Outcome Measures

- 3.1.2.1. Improvement (pain, stiffness, and functionality) as determined by the Western Ontario and McMaster Osteoarthritis Index (WOMAC) Scale at Day 7. A significant difference is observed as ≥ 2-points. See Appendix.
- 3.1.2.2. Duration of Treatment Effect/No Effect [Data Collection Tool]

### 3.1.3. Ancillary Measures (Potential measures not part of analysis)

3.1.3.1. Subject Post-Treatment Questionnaire (See Appendix)

### **3.1.4. Anticipated Observations (AO)** [Data Collection Tool]

During each visit, the area to be treated will be assessed by the investigator (observation and subject query) for the following anticipated observations (AO's). These AO's will be collected independent of adverse events.

- Bruising (ecchymosis)/Soreness
- Tingling/altered sensation (transient paresthesia/dysesthesia/anesthesia)
- Redness/inflammation (ervthema)
- Swelling
- Itching (pruritus)
- Local pain/tenderness
- Erosion/ulceration
- Eschar/crusting
- Dimpling/depression
- Hyperpigmentation
- Hypopigmentation

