### 1. Introduction

# 1.1. Background

Over 100 million patients in the United States suffer from chronic pain. Chronic pain conditions are often debilitating, taking a toll on a patient's physical and mental welfare. Though a variety of pain management techniques currently exist, the most common nonsurgical options provide slow-acting and/or short-term relief. Medication, often in the form of non-steroidal anti-inflammatory drugs (NSAIDs) and opioids, comes with an array of side effects such as nausea and vomiting. Medication also presents the possibility of more serious effects such as increased risk of heart attack and stroke, and tolerance or dependency issues. Surgical strategies tend to be reserved for more severe cases and are limited by the risks and complications typically associated with surgery including bleeding, bruising, scarring, and infection. A nonsurgical, minimally invasive, long-lasting approach to chronic pain management is desirable.

Myoscience, Inc. (Redwood City, CA) has developed a pain management device – the Cryo-Touch III – for a novel, minimally invasive procedure using focused cold therapy to target sensory nerve tissue and offer long-lasting pain relief through cryoanalgesia. The device operates on the well-established cryobiology principle that localized exposure to controlled moderately low temperature conditions can alter tissue function. The therapy treats nerves with low temperatures via a cold probe in the form of an assembly of small diameter needles, creating a highly localized treatment zone around the probe. This focused cold therapy creates a conduction block that prevents nerve signaling. Prior studies of Cryo-Touch, Cryo-Touch II, Cryo-Touch III (a.k.a. PCP 1.0) have provided preliminary evidence of effectiveness on motor nerves and have been shown to be safe with no serious device-related adverse events.

[figure not shown]
Though studies have proven efficacious in targeting motor nerves, the device's effect on sensory nerves has yet to have been investigated in the clinical setting. The goal of the study described herein is to evaluate the degree and duration of effect of the Cryo-Touch III in reducing chronic pain by targeting sensory nerves.

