### 2.6.2. Visit 2/Treatment (Day 0)

### 2.6.2.1. Pre-Treatment/Evaluation Preparation

No special preparation by the subject is required prior to the treatment. The investigator will reaffirm eligibility criteria and the subject's willingness to continue participation in the trial. Any changes in concomitant medications/concurrent procedures will be recorded. Any adverse events that may have occurred prior to treatment will be documented as a change in medical history.

Non-invasive ultrasound imaging of the treatment area may be captured. Nerve stimulation may be used to assess location of nerves via a percutaneous nerve stimulator or a transcutaneous nerve stimulator.

The Cryo-Touch III device will be used on awake subjects who are prepared with dermal anesthesia only. The skin in the treatment area will be cleansed with alcohol. Local anesthetic will be injected into target sites with the goal of complete cutaneous anesthesia at the target treatment areas prior to the treatment.

The target of treatment is the infrapatellar branch of the saphenous nerve. The nerve will be accessed by locating adjacent landmarks and treating in a linear fashion to capture the nerve as it travels inferiorly (see Figure 3).

Subjects with a bilateral indication will receive treatment in both knees.

[figure not shown]

Figure 3: Nerve map of intended treatment.

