### 2.6.2.3. Post-Treatment

Upon completion of treatment, the treatment area will be cleansed and the skin will be left undressed. Pressure to the treatment area with gauze 5-10 minutes may be applied to minimize bleeding. The subject will be instructed in post-treatment care.

The subject will be instructed to report any adverse events or treatment side effects (e.g., excessive redness, swelling, bruising, soreness, altered sensation, etc.) to the investigator between and at follow-up visits. Non-invasive ultrasound may be used to assess the volume and location of the

soft tissue treated below the dermis. Photography and videography of the treatment area may be obtained.

The subject will be scheduled and instructed for their follow-up visits and discharged from the clinic.

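### The anticipated-observation list merges numbness with tingling and dysesthesia, and bruising with soreness, so its tallies cannot give rates for the separate effects

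*Protocol*

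**What the plan says.** Section 3.1.4 of the protocol lists 11 AO entries that the investigator assesses by observation and by asking the subject. Three matter here:

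- "Tingling/altered sensation (transient paresthesia/dysesthesia/anesthesia"), a single entry for all sensory change;
- "Bruising (ecchymosis)/Soreness", a single entry for a visible sign and a symptom;
- "Local pain/tenderness", a separate entry.

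No rule says whether soreness belongs under the second or the third. The same section states: "These AO's will be collected independent of adverse events".

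Section 3 names anticipated observations among the outcome measures. Section 4.2 presents AOs as known reactions to needle passage and local anesthesia. It sends an AO to adverse event (AE) reporting under section 3.2 if the investigator judges that it goes beyond the expected response in severity or duration. Neither expectation is defined.

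On mechanism, section 1.1 says "This focused cold therapy creates a conduction block that prevents nerve signaling" and gives the study's aim as "reducing chronic pain by targeting sensory nerves". Section 2.6.2.1 adds: "The target of treatment is the infrapatellar branch of the saphenous nerve". Section 2.6.2.2 plans several treatment algorithms, grouped into cohorts for analysis.

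**The concern.** The device is meant to block conduction in a sensory nerve, so some loss of feeling in the treated area is a plausible consequence of reaching that nerve. Dysesthesia is an unwanted sensory effect. Section 3.1.4 records both, and tingling as well, under one entry.

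If one algorithm shows a higher rate on that entry than another, the tally does not say whether it produced more numbness, more tingling or more dysesthesia. These would be read differently in a study that seeks a safe and effective setting of the device. Section 1.1 says the effect on sensory nerves has not yet been studied clinically, so there is little earlier information to help interpret a combined rate.

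The bruising and soreness entry has the same weakness, with an overlap added. A subject who is sore but not bruised can be entered under either of two items, or under both.

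This is a matter of data capture. An analysis plan can choose how to report AOs, but it cannot separate components that were recorded as one.

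**Working it through.** The protocol gives no AO rate, so there is no figure to reproduce. The check compares the passages and then applies counting bounds.

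**1. What each finding maps to under section 3.1.4**

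| Finding | Entry or entries it fits |
|---|---|
| Numbness (anesthesia) | sensory entry |
| Tingling/paresthesia | sensory entry |
| Dysesthesia | sensory entry |
| Bruising | bruising/soreness |
| Soreness | bruising/soreness, or local pain/tenderness, or both |
| Local pain or tenderness | local pain/tenderness |

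**2. What leaves the joint entries.** Under section 4.2 an AO becomes an AE on grounds of severity or duration, by investigator judgement. Symptom type is not a criterion. Once it is an AE, section 3.2 asks for the diagnosis if known, so the event is identified individually. Findings judged as expected remain in the joint entry.

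**3. Bounds for the sensory entry.** Let k of n subjects have the entry. The number with dysesthesia, d, satisfies 0 ≤ d ≤ k, and the same holds for numbness and for tingling. Section 2.3 allows n up to 50; k is an assumption.

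- k = 30: 30/50 = 60%, so each component lies between 0% and 60%.
- k = 35: 35/50 = 70%, so each component lies between 0% and 70%.

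These bounds only restate that a component cannot exceed its total. They show that the tally alone gives no lower bound above zero for any one component. They do not predict what the trial will find.

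**4. Bounds for bruising and soreness.** Let a subjects have the bruising/soreness entry and b the local pain/tenderness entry.

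- Bruising: between 0 and a.
- Soreness: between 0 and min(n, a + b).
- If s subjects have soreness alone, they add between s and 2s to the sum of the two tallies, depending on how each site records them.

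**5. Size of the change.** Replacing these three entries with five takes the list from 11 to 11 − 3 + 5 = 13 entries.

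**The case against.** The strongest reply is that the protocol already has a route for the events that matter. The sensory entry is limited to transient findings, section 4.2 moves anything beyond expectation to AE reporting, and section 3.2 requires a non-directive question at each visit. Section 2.6.2.3 also tells subjects to report effects such as "excessive redness, swelling, bruising, soreness, altered sensation". This stands. A reader might infer from the joint entry that nerve-related harm cannot be told apart from the intended block, and the documents do not support that: a severe or persistent sensory harm should appear individually as an AE. The route is still incomplete, because it sorts by severity and duration against an undefined expectation. Mild or expected dysesthesia stays merged.

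Second, the data collection tool for AOs is cited but not shown, and it may already carry sub-terms, grading or free text. That also stands, so it cannot be said that the data are beyond separation. The protocol nevertheless directs assessment against the list as printed.

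Third, the protocol never uses numbness as a sign of a successful block. Effect is measured by the VAS, the WOMAC and the duration of effect. The link to the block is an inference from the mechanism and is offered only as that.

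Fourth, section 2.6.2.3 names bruising and soreness separately but keeps altered sensation as one term, and it is an illustrative instruction to subjects. It gives slight support to splitting bruising from soreness and none to splitting the sensory terms.

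Finally, section 3.1.5 places safety in AEs, SAEs and UADEs, so AOs should not be called the study's main tolerability record. They remain a named outcome.

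**Conclusion.** The point holds in a limited form. As written, the AO list does not separate numbness, tingling and dysesthesia, or bruising from soreness, and soreness fits two entries. AO tallies built on it cannot give component rates, overall or by treatment algorithm. Only events judged beyond expectation are identified individually, through AE reporting.

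The conclusion assumes that the unseen collection tool follows the printed list. If the tool already splits the entries, only the protocol text and the planned reporting need attention. The 0% to 60% and 0% to 70% ranges rest on assumed counts.

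No primary or secondary outcome and no stated figure is affected. It is a minor improvement, worth making because it is cheap.

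**What to change.** In section 3.1.4, and on the data collection tool if it does not already do so, replace the three entries with five:

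1. bruising;
2. soreness, local pain or tenderness (one entry, which removes the overlap);
3. numbness or loss of sensation;
4. tingling or paresthesia;
5. dysesthesia (unpleasant or painful sensation).

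Report each one overall and by treatment cohort.

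The cost is a short protocol edit and a net two additional entries on the form. AO data already collected under the joint entries cannot be assumed separable. They should be shown apart, labelled as combined, and not pooled with the split entries. The protocol is at revision 04, dated about eight months after its initial release, with roughly four months expected for enrollment and follow-up. Much of the AO data may therefore already exist in combined form, which would reduce the gain for this study.

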### **3.1.5. Safety Measures** [Data Collection]

Adverse events and SAEs/UADEs will be assessed at all visits. Incidence of serious adverse events (SAEs) and unanticipated adverse device effects (UADEs) will be recorded. A serious adverse event is one that meets the ISO definition of SAE (see section 4.2.1).

# 3.2. Adverse Event Reporting

Adverse events (AEs) will be assessed continuously from initiation of study treatment through study exit. An AE can be any unfavorable and unintended sign (e.g., an abnormal laboratory finding), symptom, or disease temporally associated with the use of a device, without any judgment about causality. An AE can arise from any use of the device (e.g., off-label use, use in combination with any drug) and from any route of administration including an overdose.

Timely and complete reporting of all AEs assists the Sponsor in identifying any untoward medical occurrence, thereby allowing:

- 1) protection of the safety of study subjects;
- 2) a greater understanding of the overall safety profile of the device;
- 3) recognition of device-related toxicity or ill effects;
- 4) appropriate modification of study protocols;
- 5) improvements in study design or procedures; and
- 6) adherence to worldwide regulatory requirements.

AEs may be either spontaneously reported or elicited during questioning and examination of a subject. All AEs must be completely recorded within subject's source documentation. If known, the investigator should report the diagnosis of the underlying illness or disorder, rather than its individual symptoms. Subjects experiencing AEs that cause interruption or discontinuation of participation, or those experiencing AEs that are present at the end of their participation in the study should receive follow-up as appropriate. If possible, report the outcome of any AE that caused permanent discontinuation or that was present at the end of the study particularly if the AE was considered by the investigator to be definitely, probably, or possibly related to the study device.

The investigator will instruct the subject to report any adverse events that may occur during the study. At each visit, the investigator should ask the subject, in non-directive fashion, about any change in the subject's overall condition since the previous visit.

# 3.2.1. Serious Adverse Event (SAE)/Unanticipated Adverse Device Effect (UADE)

A device-related SAE is an AE that meets the ISO definition for SAE and is rated by the investigator to be related to the study device. No device-related SAEs have been reported in prior studies of Cryo-Touch II.

Per ISO14155, an international clinical trial standard, an SAE is an AE that:

- 1 led to a death.
- 2 led to a serious deterioration in the health of the subject that
  - a. resulted in a life-threatening illness or injury,
  - b. resulted in a permanent impairment of a body structure or a body function,
  - c. required in-patient hospitalization or prolongation of existing hospitalization,
  - d. resulted in medical or surgical intervention to prevent permanent impairment to body structure or a body function.
- 3 led to fetal distress, fetal death or a congenital abnormality or birth defect

An event that is serious must be recorded on the AE worksheet and requires expeditious handling to comply with regulatory requirements.

Events NOT considered to be serious adverse events are:

- Hospitalizations for the treatment, which was elective or pre-planned, of a pre-existing condition that did not worsen, and
- Treatment on an emergency, outpatient basis for an event not fulfilling any of the definitions of "serious" given above and not resulting in hospital admission.

An **unanticipated adverse device effect** (UADE) is any of the following events that is caused by, or associated with, a device, if that effect, problem, or death was not previously identified in nature, severity, or degree of incidence in the investigational plan or application (including a supplementary plan or application):

- Any serious adverse effect on health or safety.
- Any life-threatening problem.
- Death
- Any other unanticipated serious problem associated with a device that relates to the rights, safety, or welfare of subjects.

Report of any UADEs shall be submitted to Sponsor within 24 hours of knowledge of the event.

UADEs and AEs that are classified as "serious" by the investigator or the Sponsor require expeditious handling and reporting to the Sponsor. All SAEs, whether related or unrelated to the study device, must be immediately (within 24 hours of becoming aware of the SAE) reported to the sponsor by telephone or confirmed facsimile transmission:

[name], [name], and/or Study Manager myoscience, Inc. [contact] (office) [contact] (fax)

In addition, such information should also be provided to the site's respective IRB per their governing guidelines for SAE/UADE reporting. If only limited information is initially available, follow-up reports are required. Should the investigator become aware of an SAE (regardless of its relationship to the device) that occurs within 30 days after completion of the study, the SAE must be reported in accordance with procedures specified in this protocol. In the event of death, if an autopsy is performed, a copy of the report should be sent to the Sponsor, if available.

As required, the Sponsor will notify all investigators of any UADE within 10 working days of the Sponsor's receipt of the effect.

Upon receiving such notices, the investigator must review and retain the notice and immediately submit a copy of this information to the responsible IRB according to local regulations. The investigator and IRB will determine if the informed consent requires revision. The investigator should also comply with the IRB procedures for reporting any other safety information. Where required, submission of Safety Updates by the investigator to Health Authorities should be handled according to local regulations.

### 3.3. Statistical Analysis Plan

Not Applicable.

# 4. Risk/Benefit Analysis

# 4.1. Benefits

Subjects may experience an improvement in pain post-treatment or may experience no improvement at all.

### 4.2. Risks

The Cryo-Touch III device involves percutaneous access to subcutaneous tissue using a needle and use of dermal anesthesia. Passage of a needle into the skin and delivery of local anesthesia are known and may be documented as anticipated observations (AO). See list in section 3.1.4.

These reactions do not typically require medical intervention on the part of the investigator and are usually transient. Self-care with compression or oral non-narcotic analgesics usually suffices.

In the event that an AO exceeds the expected response to the treatment, either in severity or in duration by the investigator's assessment, they will be reported as AEs per Section 3.2.

Additional adverse events which have occurred but are considered to be rare include:

- Infection/Fever
- Weakness which could result in difficulty ambulating
- Limitations in range of motion of joint
- Vasovagal reaction to needle insertion
- Burns, blistering, or scarring due to heat or cold injury

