# **Protocol Synopsis**

Title	A Prospective Non-Randomized Unblinded Study Evaluating the Treatment of Knee Osteoarthritis with the Cryo-Touch III Device		
Study Device	Cryo-Touch III (a.k.a. PCP 1.0)		
Study Objective	A proof of concept study to evaluate the feasibility of safe and effective treatment through optimization of the Cryo-Touch III device for temporary relief of pain.		
Treatment Groups	Multiple		
Duration of Study	Enrollment and follow-up is expected to take approximately 4 months. A subject will participate for approximately 10 weeks.		
Study Population	Healthy subjects, male or female, ages 18 and older with chronic knee pain related to a diagnosis of osteoarthritis of the knee.		
Total Number of Subjects	Up to 50 subjects will be enrolled.		
Number of Sites	1-2		
Inclusion Criteria	
 
Eligible subjects must meet the following criteria:
 
Male or female, 18 years of age and older.
 
Trial participants must meet American College of Rheumatology (ACR) criteria for osteoarthritis of the knee (unilateral or bilateral).
 
Any medications must be maintained on a stable schedule for at least two weeks prior to treatment. No washout period is allowed.
 
Must have an average score for pain of ≥ 4 Visual Analog Scale (VAS) over the last 30 days.
 
Subject is willing and able to give written informed consent.
 
Subject is willing and able to comply with study instructions and commit to all follow-up visits for the duration of the study.
 
Subject is in good general health and free of any systemic disease state or physical condition that might impair evaluation or which in the investigator's opinion, exposes the subject to an unacceptable risk by study participation.
 
		
Exclusion Criteria	
 
A subject is ineligible if one or more of the following criteria applies:
 
A partial or full knee replacement (in the treated knee).
 
Any use of systemic injections (in any area) within the last 6 months.
 
Current enrollment in an investigational drug or a device study that specifically targets pain treatment.
 
Any additional diagnosis that in the opinion of the investigator directly contributes to knee pain.
 
		

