### 2.6.3. Visit 3/ Maintenance (Day 7) & Visit 4/Maintenance (Day 30)

Subject will be evaluated and data collected per the schedule of events. Any changes in concomitant medications/concurrent procedures will be assessed. Any anticipated observations, adverse events, and/or SAE/UADE of the previous treatment site(s) will be assessed and documented. Non-invasive ultrasound imaging of the treatment area may be captured. Photography may be taken of the treatment area.

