# **Appendix B: Schedule of Events**

Study Activity	V1 Screening	V2 Treatment	V3	V4	V5 Phone Follow- up/EOS	
	Day -30 to Day 0	Day 0	Day 7*	Day 30*	Day 56*	
Obtain Informed Consent	X					
Review eligibility criteria	X	X				
Physical examination	X					
Medical history	X					
Concomitant medications/procedures	X	X	X	X	X	
WOMAC		X	X			
Visual Analog Scale (VAS) for pain	X	X	X	X		
Treatment		X				
AO Assessment	X		X	X	X	
Subject Post-Treatment Questionnaire		X	X	X	X	
Adverse events/procedures review		X	X	X	X	
Duration of Treatment Effect/No Effect			X	X	X	

\* A variance of +/- 3 days is allowed.

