### Day 0/Visit 2/Post-Treatment

- 1. How nervous were you during the procedure? On a scale from 1-5, 1 being extremely nervous and 5 being completely relaxed.
- 2. Prior to your treatment today, how effective or helpful was the information provided beforehand (information pamphlet, informed consent, etc.)? On a scale from 1-5, 1 being not at all effective/helpful to 5 being very effective/helpful.
- 3. Was the treatment painful? On a scale from 1-5, 1 being not at all painful to 5 being very painful.

### Visit 3/Day 7 and Visit 4/Day 30

- 1. If you any had anticipated observations (AO) from your treatment (i.e., bruising, swelling), how much did they/it impact your daily routine? On a scale from 1-5, 1 being the AO had a very negative impact to 5 being no impact at all.
- 2. Would you recommend this treatment to a friend or family member? Yes or No.
- 3. Would you have the treatment again if available? Yes or No.
- 4. Is there any pain present from the treatment? On a scale from 1-5, 1 being not at all painful to 5 being very painful.

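### Could analgesics taken after treatment pass for a device effect in the Day 7 VAS and WOMAC changes, so that the plan must say how they are handled?

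*Protocol*

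**What the plan says.** Section 3.1.1 defines the primary outcome as improvement in VAS knee pain at Day 7 against Day 0. Section 3.1.2.1 sets the WOMAC outcome at the same visit: "Improvement (pain, stiffness, and functionality) as determined by the Western Ontario and McMaster Osteoarthritis Index (WOMAC) Scale at Day 7". Neither definition mentions medication.

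The entry criterion in the Synopsis, repeated in substance in Section 2.4, is: "Any medications must be maintained on a stable schedule for at least two weeks prior to treatment. No washout period is allowed". No section extends that stability to the period after treatment.

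Section 4.2 describes the anticipated reactions as usually transient and not typically in need of medical intervention, and adds: "Self-care with compression or oral non-narcotic analgesics usually suffices". The list of reactions in Section 3.1.4 includes "Bruising (ecchymosis)/Soreness" and local pain or tenderness.

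On timing, the Appendix B footnote to the follow-up visits reads: "A variance of +/- 3 days is allowed". Appendix E, in the block for Day 7 and Day 30, asks: "Is there any pain present from the treatment".

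On recording, Section 2.6.3 states for the Day 7 and Day 30 visits: "Any changes in concomitant medications/concurrent procedures will be assessed". Appendix B schedules concomitant medications at every visit.

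Section 2.1 describes a non-randomized, unblinded study. Section 2.2 of the document's treatment description (2.6.2.2) forms cohorts by device algorithm, with no untreated or sham group. Section 3.3, the heading for the statistical analysis plan, is marked as not applicable.

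**The concern.** The stability rule protects the baseline but stops at treatment, so the seven days that define the endpoint are not covered. The protocol itself names oral analgesics as a possible response to site reactions, and those drugs can also act on knee pain. The visit window lets the reading fall as early as Day 4, when soreness from the procedure may still be present.

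In a controlled trial much of this would be shared by both arms. Here the before-after change is the only evidence of effect, and the Introduction gives the goal as judging the degree and duration of the device's effect. If many subjects started an analgesic and were helped by it, a reader could credit the device with relief that came from a tablet. Nothing in the protocol ties the medication record to the Day 7 result, and Section 3.3 does not point to another place where this would be settled.

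**Working it through.** The protocol gives no power calculation, standard deviation or expected effect, so there is no figure of its own to reproduce. The only documented inputs are the maximum of 50 subjects (Section 2.3) and the visit window (Appendix B). Everything else below is assumed, for illustration.

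**1. Timing.** The reading may be taken from 7 - 3 = Day 4 to 7 + 3 = Day 10. The early end brings it nearer to any site soreness, and the late end takes it further away.

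**2. Possible shift in the mean change.** Let *p* be the share of subjects with new or increased analgesic use and *d* the points by which it lowers their Day 7 score. The shift toward the device is *p* × *d*.
- Low end: 0.1 × 1 = 0.1 points.
- Middle: 0.2 × 1.5 = 0.30 points.
- High end: 0.4 × 2 = 0.8 points.

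A separate set of assumptions (20-50% of subjects, 0.5-1.5 points) gives nearly the same range: 0.2 × 0.5 = 0.10 to 0.5 × 1.5 = 0.75.

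**3. The opposite direction.** Subjects whose knee feels better may take less. The net shift is (*p* starting - *p* reducing) × *d*. Equal shares give 0, and the same shares with only reductions give -0.1 to -0.8. The range is therefore -0.8 to +0.8 points, with the sign unknown.

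**4. Scale against precision.** With an assumed SD of change of 2.5, the 95% half-width is t(0.975, *n* - 1) × 2.5 / √*n*.

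| Subjects analysed | Set aside | Half-width |
|---|---|---|
| 50 | 0 | 0.71 |
| 45 | 5 | 0.75 |
| 40 | 10 | 0.80 |
| 30 | 20 | 0.93 |

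Only the extreme of the assumed shift reaches the half-width at 50 subjects.

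**5. What excluding analgesic users does.** Suppose a share *p* is flagged and their observed improvement is *g* points smaller than that of the others, because people tend to take analgesics when the knee still hurts. If the others improve by *m* on average, the mean in all subjects is (1 - *p*)*m* + *p*(*m* - *g*) = *m* - *pg*. The mean without flagged subjects is *m*. Exclusion therefore raises the apparent effect by *p* × *g*. With *p* = 0.2 and *g* = 1.5 that is 0.30 points toward the device, the size of the middle case in step 2. A with-and-without comparison cannot tell a reader whether it has removed an analgesic effect or removed the failures.

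**The case for a change.** The strongest case for a change is that this is more than silence. The protocol fixes an endpoint, ends its stability rule at treatment and then mentions analgesics afterwards. It also marks its analysis section as not applicable. How later medication enters the endpoint is part of defining it, the remedy would cost two sentences and one table, and the all-subjects result would stay primary.

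Part of this stands. No section requires stable medication after Day 0, the design cannot separate the two sources of relief, and the entry in Section 3.3 weakens any appeal to a separate plan. The rest is weaker:

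- **The text of 4.2.** Oral analgesics are one of two optional forms of self-care for reactions described as usually transient. No frequency is given, and nothing says they are used around Day 7. The Appendix E question is a tolerability item put identically at Day 30, and is not evidence of analgesic use.
- **The endpoint.** The change in all treated subjects, whatever they took, is a legitimate and simple quantity for a proof-of-concept study. Sections 3.1.1 and 3.1.2.1 name an outcome and a time, and need not carry analysis rules.
- **The remedy.** Setting aside new or increased users while only counting those who cut down treats the two directions unequally, and step 5 shows how it can favor the device. It also relies on a record of uncertain detail: the revision history says the former analgesic-use endpoint was dropped because its data were not collected. That entry is context only, but it leaves open whether the general medication record can identify an increase.

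**Conclusion.** No change to the plan is needed. The Day 7 changes may partly reflect medication changes, but no stated rule or figure is wrong, and the gap is one analysts can fill from a record already scheduled for Day 7. The possible effect is -0.8 to +0.8 points on the mean, resting entirely on assumed shares of 10-40% and assumed effects of 1-2 points. The documents support neither a size nor a sign.

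Figures for a false claim of success add little. With no device effect and 50 subjects, the chance of a nominally significant improvement runs from about 5% to 76% across 20-50% use, 0.5-1.5 points and SDs of 2.0-2.5. That presumes a test the protocol does not state and shifts in one direction only.

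An analyst who wishes to can tabulate new, increased and reduced analgesic use between Day 0 and Day 7, as far as the record allows, treating both directions alike. That is a reporting choice, and it would not resolve attribution, which is limited mainly by the absence of a control group.
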